5. STUDY DESIGN

5.1. Study Overview

5.1.1. Part 1

Part 1 is a Phase 1/2, randomized, double-blind, placebo-controlled, MAD evaluation of the safety, tolerability, and PK of BIIB105, administered IT to approximately 98 participants (76 participants with ALS and 22 participants with polyQ-ALS) at approximately 15 sites globally. Cohorts A, B, C1, and C2 will receive up to 5 doses over approximately 3 months. Cohorts D1 and D2 will receive up to 8 doses over approximately 6 months.

Approximately 98 participants are planned to be randomized in Part 1. Participants who withdraw may be replaced in a cohort at the discretion of the Sponsor. With potential replacement, approximately 108 participants could be randomized.

Adult participants with ALS will be randomized at a ratio of 3:1 (active drug:placebo) in Cohorts A, B, C1, and D1. Adult participants with polyQ-ALS will be randomized at a ratio of 3:1 in Cohort C2 and at a ratio of 2:1 in Cohort D2. Cohorts C1 and C2 can dose concurrently. Cohorts D1 and D2 can dose concurrently.

If dosing stops at one of the lower dosing cohorts, the cohort with the highest tolerated dose may be expanded to include an additional 20 participants with ALS (3:1, active drug:placebo) and an additional 18 participants with polyQ-ALS (2:1, active drug:placebo).

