5.3. Dosing

5.3.1. Dose Escalation (Part 1)

For each dose escalation, safety (AEs/SAEs, vital signs, ECGs, and laboratory parameters) and available PK data will be reviewed. The proposed dose escalation is illustrated in Figure 1 and the proposed dosing groups are as follows:

Participants with ALS:

Cohort A: BIIB105 5 mg (6 participants) or placebo (2 participants)

Cohort B: BIIB105 20 mg (6 participants) or placebo (2 participants)

Cohort C1: BIIB105 60 mg (9 participants) or placebo (3 participants)

Cohort D1: BIIB105 120 mg (approximately 36 participants) or placebo (approximately 12 participants)

Participants with polyQ-ALS:

Cohort C2: BIIB105 60 mg (3 participants) or placebo (1 participant)

Cohort D2: BIIB105 120 mg (approximately 12 participants) or placebo (approximately 6 participants)

See Section 3.1.2 for details regarding the rationale for the starting dose and dose escalation.

After a cohort (Cohorts A, B, C1, and C2) is fully randomized and at least 36 days have elapsed since the randomization and dosing of the eighth participant, a Sponsor SST will hold a dose escalation meeting to review all available blinded safety data from all randomized participants. There must be a minimum of 6 evaluable participants for the dose escalation meeting to occur. In Cohort C2, all 4 participants must be evaluable for the dose escalation meeting to occur. Evaluable participants are defined as those who have completed 3 dosing visits and the Day 36 CV. This CV occurs 1 week after the Day 29 dose, the dose that is projected to result in the targeted steady-state exposures for the cohort. Dosing of Cohort D1 is dependent on the SST approving the safety of Cohort C1, and dosing of Cohort D2 is dependent on an SST approving the safety of Cohort C2.

For Cohort D1, the safety review will occur after the cohort is fully randomized, and at least 92 days have elapsed since the randomization and dosing of the 36th participant. The SST will review all available blinded safety data from all randomized participants in the cohort, which must include a minimum of 33 evaluable participants (those who completed all of the first 5 dosing visits as well as the Day 92 clinic visit). This review will be for a final safety review for Cohort D1. Should Part 1 be terminated early (per Section 5.2.1 and Section 13.4) prior to reaching randomization of the entire D1 cohort or minimal evaluable criteria as defined, a final

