3.5. Treatment Group

In the integrated safety and PK summary of Part 1 and Part 2, summaries and analyses will be presented by treatment received for the subjects in the safety population defined previously. The following treatment group will be considered for the safety data:

- BIIB105 Pool 120 mg DL: this group includes Cohorts D1 and D2 participants who received at least one dose of BIIB105 120 mg in Part 1 or Part 2, i.e. total of all subjects in Part 1 Cohorts D1 and D2 exposed to BIIB105 120 mg during Part 1 (i.e. DL1) or initiated during Part 2 (DL2). Data since their first dose of BIIB105 120 mg will be included.
- BIIB105 Pool 60 mg: this group includes the participants who received at least one dose of BIIB105 60 mg in Part 1 or Part 2. The 60 mg dose in Part 2 was increased to 120 mg starting December 2023. Data since their first dose of BIIB105 60 mg and before their first dose of 120 mg will be included in analysis for this pool. Baseline is defined as first dose of BIIB105 60 mg.
- BIIB105 Pool 120 mg: this group includes the participants who received at least one dose of BIIB105 120 mg in Part 1 or Part 2. Data since their first dose of BIIB105 120 mg will be included. Baseline is defined as first dose of BIIB105 120 mg. In addition to participants from BIIB105 Pool 120 mg DL, this group will also include Cohort A, B, C1, and C2 participants who received at least one dose of BIIB105 120 mg in Part 2, i.e. participants escalated from 60 mg to 120 mg in Part 2.

In the integrated efficacy and biomarker summary of Part 1 and Part 2 for D1 and D2, pooled group “DL” includes cohorts D1 and D2 subjects in Part 1 clinical function population or PD population and data since their first dose of study drug treatment in Part 1 will be included. The following treatment group will be considered for the efficacy data:

- Placebo/Delayed-start BIIB105 120 mg: this group includes the Cohorts D1 and D2 subjects in the Part 1 FAS population who were on placebo in Part 1, who may or may not roll over to Part 2 and start active treatment with BIIB105. Data since their first dose of study drug treatment in Part 1 will be included. Baseline is defined as the Day 1 of Part 1.

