Missing data for postbaseline assessments will be imputed using the multiple imputation method [Schafer 1997, Schafer 1999]. Visit windowing as described in Section 4.5 will be applied prior to any imputations. Any imputation on an item level within a scale will be performed prior to performing MI.

MI will be performed on actual values, domains, total scores or summary scores depending on the endpoint and not performed at the item level; the complete datasets can then be used to calculate change from baseline.

All available data will be used where subjects have missed doses but continued to perform assessments; otherwise any missing values will be imputed using MI. The Markov Chain Monte Carlo (MCMC) will be used to impute the missing postbaseline scores in the endpoint by treatment group.

Prior to performing multiple imputation, the dataset will be sorted by ascending unique subject identifier (USUBJID). The treatment variable will be coded so that early-start BIIB105 120 mg is set to 0 and placebo/delayed-start BIIB105 120 mg is set to 1 for inclusion in the MI model. Similarly, two level riluzole/edaravone use will be set to 0 for

CONFIDENTIAL

The information contained herein may not be used, disclosed, or published without the written consent of
Biogen MA Inc.

no use (i.e. neither riluzole or edaravone) and 1 for use of either riluzole or edaravone or both. When three level riluzole/edaravone use is used, two binary variables (edaril3cat1 and edaril3cat2) will be coded, where both variables will be set to 0 for no use (i.e. neither riluzole or edaravone), edaril3cat1 is set to 1 and edaril3cat2 is set to 0 for use of riluzole only, and edaril3cat1 is set to 0 and edaril3cat2 is set to 1 for edaravone use. The variable list in the model for imputations will include treatment group, riluzole/edaravone use, the corresponding baseline value for the endpoint, and all available postbaseline values. The MI model will be performed by treatment group. A set of 100 complete imputed datasets will be generated. This number of imputed datasets needs to be large enough for applying the multiple imputation method in this study as the sample size is small. The relative efficiency parameter will also be checked to determine the acceptability of the imputed results i.e. it should be close to 98% or higher. The seed used for the multiple imputation is specified in [Table 2](#).

Table 2: Seed used for each endpoint in MI

Endpoint	Seed

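### Integrated SAP: the imputation is specified both by arm and with treatment as a model variable; run by arm, the ALSFRS-R model has too many variables for the planned delayed-start group of about 18

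*SAP*

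**What the plan says.** All of this is in the SAP for Part 2 and the integrated analysis (version 1.0, 5 September 2024), mainly in the multiple-imputation part of Section 5.6.1.

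- **By arm, stated twice.** "The Markov Chain Monte Carlo (MCMC) will be used to impute the missing postbaseline scores in the endpoint by treatment group". Later, after the variable list: "corresponding baseline value for the endpoint, and all available postbaseline values. The MI model will be performed by treatment group".
- **Treatment as a model variable, also stated twice.** Early-start is coded 0, and delayed-start "is set to 1 for inclusion in the MI model". Then: "The variable list in the model for imputations will include treatment group". The list continues with riluzole/edaravone use (one or two binary variables), baseline and the postbaseline values.
- **Quality check.** There are 100 imputed datasets, and of the relative efficiency the SAP says "it should be close to 98% or higher".
- **Who is in the smaller arm.** For Placebo/Delayed-start, Section 3.5 says "this group includes the Cohorts D1 and D2 subjects in the Part 1 FAS population who were on placebo in Part 1".
- **Use of the result.** Section 5.6.2 takes the Week 40 early- versus delayed-start difference in ALSFRS-R from these imputed data. Each of the four functional domains has its own imputation model, and the total is built from them.

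No informative or ridge prior, reduced visit set or fallback rule appears in the visible text.

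**The concern.** There are two linked problems.

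First, the instructions conflict. Within one arm the treatment code is a constant, so a by-arm model cannot use it. A pooled model can use it, but is then not run by arm. Two programmers could follow this section and build different models.

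Second, the by-arm reading puts nearly every ALSFRS-R visit into a multivariate normal model for a very small group. The section itself acknowledges the small sample, but responds only with more imputations. That reduces simulation error and does nothing for a covariance matrix that cannot be estimated.

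The Week 40 ALSFRS-R comparison, a key endpoint listed in Section 2.1, rests on this step. As written, the analyst must decide how to make the model run. That decision would come after the unblinded interim (database lock 29 April 2024, Section 4.1) and without a rule to follow.

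**Working it through.** **Planned sizes.** The delayed-start number is not stated, so it is built from the cohorts in Protocol Section 5.3.1. For D1 the plan is about 36 active and 12 placebo; for D2, "BIIB105 120 mg (approximately 12 participants) or placebo (approximately 6 participants").

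- Check on the cohort counts: placebo in A, B, C1 and D1 = 2 + 2 + 3 + 12 = 19, the pooled placebo N in Protocol Section 13.5. All cohorts: 8 + 8 + 12 + 48 + 4 + 18 = 98, as stated.
- Delayed-start: 12 + 6 = 18. Early-start: 36 + 12 = 48. Both: 66.

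**Variables in one ALSFRS-R domain model to Week 40** (SAP Section 3.1, visit tables)

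- Part 1 postbaseline visits: Weeks 4, 5, 8, 9, 12, 13, 16, 17, 20, 21, 24, 25 = 12.
- Part 2 visits to Week 40: Weeks 28, 32, 36, 40, plus Week 30 if kept = 4 or 5.
- Baseline: 1. Riluzole/edaravone indicators: 1 or 2.
- Minimum 12 + 4 + 1 + 1 = 18; maximum 12 + 5 + 1 + 2 = 20.
- If the use indicator is constant within the arm: 12 + 4 + 1 = 17, or 12 + 5 + 1 = 18.

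Week 40 is a lenient cut-off, because the variable list is not capped there. Adding Weeks 44, 48 and 52 gives 21 to 23.

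**Estimability.** The sample covariance of n complete records has rank at most n − 1. An unrestricted covariance of p variables therefore needs n ≥ p + 1, and the spare degrees of freedom are n − 1 − p.

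| Model | n | Rank limit | p | Spare |
|---|---|---|---|---|
| Delayed-start, by arm | 18 | 17 | 18–20 | none; short by 1 to 3 |
| Same, use indicator constant | 18 | 17 | 17–18 | 0, or short by 1 |
| Delayed-start, proportional replacement | 20 | 19 | 18–20 | 1, 0, or short by 1 |
| Early-start, by arm | 48 | 47 | 18–20 | 27–29 |
| Pooled, treatment included | 66 | 65 | 19–21 | 44–46 |

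A numerical rank check agrees: at n = 18 the rank is 17 for 18, 19 or 20 variables; at n = 48 and 66 it is full.

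The replacement row uses Protocol Section 5.1: "With potential replacement, approximately 108 participants could be randomized". Spread in proportion, 18 × 108/98 = 19.8. In the extreme case that all 10 extra participants fell in this arm, n = 28 and 18 to 20 variables would leave 7 to 9 spare.

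These counts assume complete data, which is the most favourable case.

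**Other endpoints by arm, treatment removed**

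- SVC: 7 Part 1 visits + 4 or 5 + 1 + 1 or 2 = 13 to 15.
- HHD: 6 + 2 or 3 + 1 + 1 or 2 = 10 to 12.

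Both are below 17.

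**Relative efficiency.** With m imputations and fraction of missing information λ, it is 1/(1 + λ/m). At m = 100 and the worst case λ = 1, it is 1/1.01 = 99.0%. A threshold of 98% cannot be missed, whatever the state of the model.

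**The case against.** The strongest reply is that the conflict is only leftover wording. By-arm imputation is stated twice, a constant code carries no information, and deleting the coding sentence would settle the matter. As a reading of intent this is fair. It does not rescue the ALSFRS-R model, because the by-arm reading is the one that runs out of rank.

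Several qualifications stand:

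- The planned sizes are approximate, and the number actually in the delayed-start arm is not given.
- The count of 18 to 20 needs at least one riluzole/edaravone indicator to vary within that arm, which the documents do not show.
- The failure applies to an unrestricted covariance. A ridge or informative prior could make the model run, but none is stated.
- Table 3 speaks of selected time points for the imputed ANCOVA, which could hint at a smaller visit set. It reads more naturally as a description of what is reported, and the variable list itself takes every available visit.
- The stakes are limited. The study had been stopped, the stated objective of this analysis is safety, and the report is abbreviated.

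The imputation uses all available data, so participants who drop out still contribute their observed visits. Subtracting them one for one from the degrees of freedom would overstate the loss; no such deduction is made here.

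**Conclusion.** The point holds in a conditional form. The specification contradicts itself on whether imputation is by arm or pooled. If by arm, the delayed-start ALSFRS-R model to Week 40 is short of rank by 1 to 3 at the planned size. In the most favourable count (no varying use indicator, Week 30 left out), it fits with nothing to spare. This rests on about 18 delayed-start participants, an unrestricted covariance and no prior. The relative-efficiency criterion gives no protection.

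A reader might infer three stronger things that the documents do not support:

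- **That the reported Week 40 ALSFRS-R result is invalid.** Neither the actual arm size nor the model actually run is shown; around 20 participants would allow 18 or 19 variables, barely.
- **That all the efficacy imputations fail.** The early-start arm, SVC and HHD are not rank-deficient once treatment is taken out of the by-arm list.
- **That the between-dose visits must be dropped.** The pooled model is estimable with every scheduled visit to Week 40.

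It should be fixed, because the endpoint is listed as key and the correction is cheap. It does not bear on the safety conclusions.

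**What to change.** **Preferred.** In Section 5.6.1, delete the by-treatment-group instruction in both places. Impute in one model over both arms, with treatment, riluzole/edaravone use, baseline and all scheduled visits up to the latest time point analysed. For ALSFRS-R to Week 40 this is 19 to 21 variables on about 66 planned participants. To Week 52 it would be 22 to 24 variables, leaving 65 − 24 = 41 to 65 − 22 = 43 spare on complete data. The separate model for each domain can stay.

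**If by-arm imputation is kept.** Remove treatment from the coding sentence and the variable list. For ALSFRS-R, state either a reduced visit set or a ridge prior.

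Either way, record the change in the SAP version history, with date and reason, as made after the unblinded interim.

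**Cost.** SAP text and modest reprogramming; no new data. The pooled model assumes a common covariance in the two arms. Because the same paragraph governs SVC and HHD, they would be imputed in pooled form too. The change is also made with interim results known, which is why it should be documented openly.

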ALSFRS-R Bulbar function Respiratory function Fine motor skills Gross motor skills (Total score will not be imputed separately; instead the imputed datasets from the functional domains will be used to calculate the total score. A separate model will be used for each functional domain.)	8492382
Percent predicted SVC	6734934
HHD megascore (overall, upper extremities, lower extremities)	3748311
[REDACTED]	[REDACTED]
[REDACTED] [REDACTED] [REDACTED]	[REDACTED]
[REDACTED]	[REDACTED]

Imputed values that are outside of the expected range of a scale will be reset: for example, for ALSFRS-R bulbar function should only be in the range 0 to 12. Values outside of this

CONFIDENTIAL

The information contained herein may not be used, disclosed, or published without the written consent of
Biogen MA Inc.

range will be reset so that values below 0 are set to 0 and values above 12 are set to 12. Values will be used as imputed, and will not be rounded prior to analysis.

For each of the 100 imputed datasets, change from baseline will be calculated using the imputed datasets, and the change from baseline endpoint will be compared between treatment groups using an ANCOVA model for continuous endpoints (efficacy and pharmacodynamic endpoints). The ANCOVA model will include covariates for each of the corresponding baseline value for the endpoint, baseline plasma NfL, baseline disease duration since symptom onset, and use of riluzole or edaravone. The model will be used to present overall LS means and standard errors for each treatment group, and LS mean differences for treatment with corresponding 95% CI and p-values. A combined estimate of the LS means, LS mean differences and standard errors of the 100 imputed datasets will be obtained, where standard errors will be used to obtain 95% CI from PROC MIANALYZE [Little et al, 2002]. Separate ANCOVA models will be used to obtain estimates, 95% confidence intervals and p-values for other visits. For subjects who died, the imputed values after death will be used in the ANCOVA analysis eg change from baseline in ALSFRS-R.

For integrated analyses of Part 1 and Part 2 for Cohorts D1 and D2, ANCOVA model will be performed for Early-start BIIB105 120 mg vs. Placebo/Delayed-start BIIB105 120 mg.

Presentation of Data

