Endpoint	Summary/ Analysis	Part 2	Integrated Part 1 and Part 2
		BIIB105 60 mg	Pool DL (Placebo/delayed-start BIIB105 120 mg And Early-start BIIB105 120 mg)
Absolute value/change in ALSFRS-R total score since Part 1 baseline	Observed data all visits descriptive		x
Absolute value/change in ALSFRS-R total score since Part 2 baseline	Observed data all visits descriptive	x	
Change in ALSFRS-R total score by selected time points since Part 1 baseline	MI data + ANCOVA		x
Absolute value/change in percent predicted SVC since Part 1 baseline	Observed data all visits descriptive		x
Absolute value/change in percent predicted SVC since Part 2 baseline	Observed data all visits descriptive	x	
Change in percent predicted SVC by selected time points since Part 1 baseline	MI data + ANCOVA		x
Absolute value/change in HHD megascore since Part 1 baseline	Observed data all visits descriptive		x
Absolute value/change in HHD megascore since Part 2 baseline	Observed data all visits descriptive	x	
Change in HHD megascore by selected	MI data + ANCOVA		x

CONFIDENTIAL

The information contained herein may not be used, disclosed, or published without the written consent of
Biogen MA Inc.

time points since Part 1 baseline			
Time to event endpoints since Part 1 baseline	K-M plot Cox model		x

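### ALSFRS-R domains are imputed in unlinked models and then summed, so the Week 40 standard error of the total can be too large or too small, depending on seed handling the SAP does not state

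*SAP*

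**What the plan says.** All references are to the final SAP for Part 2 and the integrated analysis (version 1.0, 05 September 2024) unless stated.

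- Section 5.6.1, multiple imputation: missing postbaseline scores are imputed by MCMC. The variables are treatment group, riluzole/edaravone use, "the corresponding baseline value for the endpoint, and all available postbaseline values". Also: "The MI model will be performed by treatment group" and "A set of 100 complete imputed datasets will be generated". Relative efficiency is the acceptability check: "it should be close to 98% or higher".
- Section 5.6.1, Table 2 (imputation seeds): the ALSFRS-R row names the four domains and gives one seed, 8492382. It adds: "Total score will not be imputed separately; instead the imputed datasets from the functional domains will be used to calculate the total score". It then says "A separate model will be used for each functional domain".
- Table 3: the row "Change in ALSFRS-R total score by selected time points since Part 1 baseline" is analysed by multiple imputation and ANCOVA. No domain score has such a row.
- Section 5.6.2, Statistical Analyses: the Week 40 early-start versus delayed-start difference, standard error and 95% CI come from that ANCOVA. Section 5.6.1 adds p-values.
- Section 5.6.2, Missing Data: says that missing data at a visit are not imputed.
- Protocol 13.3.4 allows imputation of domains or of total scores, depending on the endpoint.

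**The concern.** The variance of a sum depends on how its parts move together. Section 5.6.2 prorates the total when up to three items are missing, so what is left for multiple imputation is mainly whole visits, with all four domains absent together. That is where the missing covariance matters.

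Two programmers could follow this SAP faithfully and differ. One lets a single random stream run on through the four models, so the imputed residuals are independent across domains and the total varies too little. The other restarts 8492382 for each domain. With the same sort order, variables and missing pattern, the same random deviates then drive all four domains and the total varies too much. The standard error, interval and p-value for a protocol secondary endpoint would differ between them.

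**Working it through.** **1. Inputs.** The visible documents give no Week 40 standard error, SD, between-domain correlation or missing fraction, and the dropout rate is redacted, so there is no stated figure to reproduce. Planned sizes from Protocol 5.3.1 are 36 + 12 = 48 early-start and 12 + 6 = 18 delayed-start. Correlation, missing fraction and time covariance below are assumptions.

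**2. Closed form.** Take a participant missing all four domains, with equal domain residual variance s² and residual correlation ρ. The residual variance of the total is:

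- true: 4s²(1 + 3ρ)
- independent streams: 4s², a ratio of 1/(1 + 3ρ)
- fully shared deviates: 16s², a ratio of 4/(1 + 3ρ)

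At ρ = 0.3 the ratios are 1/1.9 = 0.53 and 4/1.9 = 2.11. At ρ = 0.5 they are 1/2.5 = 0.40 and 4/2.5 = 1.60.

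**3. Does the SAP's check catch this?** Relative efficiency is 1/(1 + λ/m), where λ is the fraction of missing information. With m = 100 and the worst case λ = 1, it is 1/1.01 = 0.990. The check passes whatever the covariance error.

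**4. Simulation.** 48 vs 18 participants, 400 trials per setting, 100 imputations, Bayesian regression imputation by arm, ANCOVA of the total on baseline total, and Rubin pooling. Data were normal at five visits (Weeks 0 to 40), with monotone dropout completely at random and no resetting to 0-12. Each cell gives mean standard error / empirical SD of the estimate, the relative difference, and 95% CI coverage.

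| ρ, missing | Total imputed directly | Domains, independent streams | Domains, seed restarted |
|---|---|---|---|
| 0.3, 15% | 1.910/1.807, +6%, 96.0% | 1.801/1.802, 0%, 94.3% | 2.104/1.793, +17%, 97.8% |
| 0.3, 30% | 2.110/1.956, +8%, 96.0% | 1.883/1.943, -3%, 93.5% | 2.450/1.950, +26%, 99.3% |
| 0.3, 45% | 2.523/2.305, +9%, 97.3% | 2.114/2.226, -5%, 93.5% | 3.057/2.230, +37%, 99.0% |
| 0.6, 15% | 2.323/2.200, +6%, 96.0% | 2.137/2.191, -2%, 93.8% | 2.412/2.181, +11%, 96.5% |
| 0.6, 30% | 2.565/2.408, +7%, 96.5% | 2.181/2.394, -9%, 93.0% | 2.718/2.399, +13%, 98.0% |
| 0.6, 45% | 3.054/2.806, +9%, 97.8% | 2.352/2.690, -13%, 92.5% | 3.308/2.701, +22%, 98.5% |

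Monte Carlo error of an empirical SD from 400 trials is about 1/√(2 × 399) = 3.5%, so the smallest differences are within noise.

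A separate run (500 trials, 30% missing, ρ = 0.3-0.5, Monte Carlo error about 3%) agrees. A restarted seed gave a standard error 17-30% too large (coverage 98-99%), and independent streams one 3-6% too small (coverage 94-95%). Over the two runs, direct imputation was about 7-11% conservative at 30% missing.

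**5. Reading the table.** Direct imputation runs somewhat high in these small samples. Measured against it, the independent-stream standard error is 10.8% lower at ρ = 0.3 and 15.0% lower at ρ = 0.6 (30% missing). The general upward tendency offsets part of this, which is why the shortfall against the empirical SD is only 3-9%. At ρ = 0 with independent streams, the two methods agree within 0.6%. The empirical SDs differ little across methods (1.943-1.956 at ρ = 0.3, 30% missing), so the fault lies in the standard error, not in the spread of the point estimate.

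**The case against.** The strongest reply is that the large figures rest on a coding choice the SAP does not make. One seed in one table row need not mean a restart for each domain. That stands: the documents are silent, so neither direction can be asserted.

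Second, domain imputation with independent streams performs tolerably. At ρ = 0.3 and 30% missing it is nearer the empirical SD (-3%) than direct imputation (+8%). That also stands for that setting. At ρ = 0.6 the comparison is -9% against +7%, and only direct imputation kept coverage at or above nominal throughout.

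Third, a restarted seed is conservative and creates no false positives. True, but it wastes precision in a comparison with 18 planned participants in one arm.

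Fourth, the consequence is limited. The study was stopped early, the report is abbreviated, the stated objective of the final analysis is safety, and no visible decision rule uses this interval. Integrated unblinded results had already been analysed (Section 4.1), so changing the method needs a documented reason. This limits the weight of the point but does not remove it, because the interval and p-value are still planned.

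A reader might infer that all between-domain correlation is lost. It is not: observed totals keep it, and imputed values inherit part through each domain's own history. A reader might also infer that the treatment estimate is biased, or that resetting domain values to 0-12 distorts the contrast. The simulation shows little effect on the estimate under random dropout, and the documents give no domain distributions from which a resetting effect could be sized.

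**Conclusion.** The point holds in conditional form. As written, the plan does not preserve residual between-domain covariance for missed visits and does not say how the seed is used. The Week 40 standard error of the ALSFRS-R total is overstated by about 10-30% if the seed is restarted on a common missing pattern (ρ about 0.3-0.6, 15-30% missing). With independent streams it is understated by about 3-9% at 30% missing, and by more at higher missingness. The covariance error is nil with no missing data, or with independent streams and zero residual correlation.

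It would go too far to say that the standard error is known to be wrong in a given direction or by a given amount. Missingness and correlation are not in the documents, and the simulations assume normal data, random dropout and a simpler ANCOVA than planned. The change is worth making because it is cheap and the SAP's own check cannot reveal the problem.

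**What to change.** In the seed table of Section 5.6.1, impute the ALSFRS-R total in one model, with one seed and a 0-48 range, for the Week 40 ANCOVA. Protocol 13.3.4 already permits this, and no planned domain-level ANCOVA needs the domain imputations. The cost is a table edit, less programming, and a mildly conservative standard error (about 7-11% in simulation at 30% missing). Because integrated results had already been seen, record the reason for the change.

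If domain imputation is kept, assign each domain its own seed, state this, and report direct imputation of the total as a sensitivity analysis. A joint four-domain model is not a practical alternative. To Week 40 there are about 17 postbaseline visits per domain (12 in Part 1 and 5 in Part 2), so 4 × 17 = 68 values against 18 planned delayed-start participants. Even a single-score model by arm is tight on that count, so list the visits that enter it.

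Also reconcile the Section 5.6.2 statement that missing visit data are not imputed with the multiple-imputation ANCOVA in the same section, for example by limiting it to the descriptive summaries.
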